NCT04111068

Official Title: Improving Vision in Adults With Macular Degeneration, Study 1: the Effect of Brain Stimulation

Date Last Updated: February 4, 2022

Statistics Analysis Plan

Planned Study Components

- A. Independent Variables:
 - 1. Stimulation Type (active vs sham)
 - 2. Test Time (effect during, effect 5 mins post, effect 30 mins post)
 - For statistical testing, Test time will contain 3 levels, defined as:
 - i. During stimulation baseline
 - ii. 5 mins post stimulation baseline
 - iii. 30 mins post stimulation baseline
- B. Experimental Design and Outcome Measures:
 - 1. 2 (Stim type) x 3 (Test time) analysis: Outcome is Crowded VA in logMAR (FrACT)
 - 2. 2 (Stim type) x 3 (Test time) analysis: Outcome is Uncrowded VA in logMAR (FrACT)
 - 3. 2 (Stim type) x 3 (Test time) analysis: Outcome is RSVP reading analysis
- C. *Interactions:* An interaction between stim type and test time indicates that active stimulation was effective, but not at every timepoint. Therefore, the planned contrast in the event of an interaction:
 - 1. Active vs. sham: individually compare active vs sham at the three timepoints.
- D. Covariates to examine:
 - 1. Language, primary analysis (dichotomous)
 - 2. Age (continuous)
 - 3. Distance visual acuity (will be dichotomized)^a
 - 4. RSVP critical print size (will be dichotomized)^a
 - 5. RSVP maximum reading speed (will be dichotomized) ^a
 - 6. Cognitive Screening: MoCA-blind (UW) and (HKPU) (will be dichotomized) ^b
 - 7. Type of AMD: wet, dry (dichotomous) ^c
 - a. Because the different languages likely elicit different mean performances, covariates listed will be dichotomized with a median split separately for each language to allow combined data analysis with the included covariate. The "low" group will include any participants scoring the median. The "high" group will include only participants scoring better than the median.
 - b. Cognitive Screening will be dichotomized separately for each language along standard thresholds for clinical significance. This covariate will only be tested if at least 5 total participants are allocated to both groups.
 - c. Type of AMD will only be tested if at least 5 total participants are allocated both groups.
- E. Additional Details:
 - 1. The analysis will be run individually for each planned outcome measure.
 - 2. Participants with incomplete data will be excluded from the analysis
 - 3. All tests will be 2-tailed with alpha = 0.05

Analysis Procedure

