- 1. Normality check: Check if ANOVA assumptions are violated (languages combined)
 - 1. Sphericity of variances use Mauchly's Test of Sphericity to check for significant violations of sphericity.
 - Normality of Residuals visually inspect pp plot and qq residual plots evaluate the degree of violation.
 - If sphericity assumption is violated: Use Greenhouse Giesser correction for all main effects and interactions, following *Parametric Statistics*, section 2a
 - If interaction between independent variables is significant: Use Wilcoxonsigned-rank tests for planned pairwise comparisons instead of ttests.
 - If normality assumption is violated: follow *Nonparametric Statistics*, section 2b.

2a. Parametric Statistics

- 1. Primary Analysis:
 - i. Perform repeated-measures ANCOVA, with Language as covariate.
 - If interaction between stimulation type and test time is significant:
 - ii. Examine planned comparisons with within-subject ttests

If language covariate is significant or significantly interacts with another factor:

iii. Run separate repeated-measures ANOVAs for each language

If either ANOVA reveals an interaction:

- iv. Examine planned pairwise comparisons with within-subject ttests
- 2. Secondary Analysis:
 - i. Perform repeated-measures ANCOVA, iteratively with each secondary covariate to be tested.

If interaction between stimulation type and test time is significant:

ii. Examine planned comparisons with within-subject ttests

If any dichotomous covariate is significant or significantly interacts with another factor: iii. Run separate repeated-measures ANOVAs for each level of the covariate

If either ANOVA reveals an interaction:

iv. Examine planned pairwise comparisons with within-subject ttests

2b. Nonparametric Statistics

- 1. Primary Analysis:
 - i. Perform aligned rank transform for nonparametric ANOVA with 3 independent factors.
 - 2 (Stim type) x 3 (test time) x 2 (language) mixed effects ANOVA

If stim type and test time interact, but language is not significant and no interaction involving language occurs:

ii. Run planned pairwise comparisons using Wilcoxon-signed-rank tests

If language is significant or if language significantly interacts with any other factor:

iii. Discard previous analysis and run two separate ART-transformed 2 (stim type) x 3 (test time) nonparametric ANOVAs, one for each level of language.

If either ANOVA reveals an interaction:

iv. Run planned pairwise comparisons with Wilcoxon-signed-rank tests

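### Secondary covariates: the within-language median split gives up sensitivity without need in the parametric ANCOVA, and the nonparametric route has no method for continuous age

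*SAP*

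**What the plan says.** SAP section D lists one primary covariate, language, and six secondary ones. Age is listed as continuous. Distance visual acuity, RSVP critical print size and RSVP maximum reading speed fall under note a, which says that the "covariates listed will be dichotomized with a median split separately for each language to allow combined data analysis with the included covariate". Its reason is "Because the different languages likely elicit different mean performances".

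Note b, on cognitive screening, adds "This covariate will only be tested if at least 5 total participants are allocated to both groups". Note c reads "Type of AMD will only be tested if at least 5 total participants are allocated both groups".

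The secondary step of 2a is "Perform repeated-measures ANCOVA, iteratively with each secondary covariate to be tested". Its rerun clause begins "If any dichotomous covariate is significant or significantly interacts with another factor", so age is exempt from reruns there.

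In 2b the primary model is an aligned rank transform (ART) analysis, specified as "2 (Stim type) x 3 (test time) x 2 (language) mixed effects ANOVA". If language matters, it is followed by separate analyses for each language. The secondary step of 2b applies this same procedure to every covariate and makes no exception for age. The choice between 2a and 2b rests on visual inspection of residual plots.

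**The concern.** There are two substantive gaps, both confined to the secondary covariate analyses.

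First, a difference in means between languages can be removed without a split. Within-language standardisation or a language term does it and keeps the ordering and spacing of the values. Because 2a accepts a continuous covariate, the split there discards information for a reason that does not require it. Section 2a acts on a covariate's significance and on its interactions, so lower sensitivity also changes which follow-up analyses are run.

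Second, a continuous variable has no levels. Section 2b therefore has no defined model for age and nothing to rerun by level. If an outcome goes to 2b, the method for age would have to be chosen after the residual plots have been seen.

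A smaller matter is that the floor in notes b and c can be read as five in each group or five in all.

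**Working it through.** **Inputs from the documents.** Two-sided alpha of 0.05, the split rule, age as continuous, and the floor of five. There is no sample size, power or covariate effect size, so there is no planned figure to reproduce.

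**Assumptions.** n = 20, 30 or 40; two equal language groups; normal errors; language in the model (2a does not say that language stays in the secondary ANCOVAs). r is the within-language correlation between the covariate and each participant's active-minus-sham difference averaged over the three test times.

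**Step 1: reduce the 2a test to one score.** In a simulated 2 x 3 repeated-measures ANCOVA (n = 24), F for stimulation-by-covariate was 1.58492. The squared t from regressing the averaged difference on language and covariate was also 1.58492. The one-score regression is therefore the same test.

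**Step 2: check by hand.** A median split of a normal covariate correlates √(2/π) = 0.798 with the original, so it keeps 2/π = 0.637 of the linear information. Take n = 30 and r = 0.49, with power ≈ Φ(atanh(r)·√(n − 4) − 1.96):

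- continuous: 0.536 × 5.099 − 1.96 = 0.773, power 0.78
- split: r = 0.49 × 0.798 = 0.391; 0.413 × 5.099 − 1.96 = 0.146, power 0.56

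**Step 3: simulate** (4,000 to 6,000 runs per setting in most cases; ranges are over the values of n).

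| Covariate and effect (assumed) | Continuous | Split |
|---|---|---|
| Normal, linear, r = 0.2 | 0.12-0.24 | 0.10-0.16 |
| Normal, linear, r = 0.3 | 0.24-0.47 | 0.15-0.30 |
| Normal, linear, r = 0.59, 0.49, 0.43 at n = 20, 30, 40 | 0.79-0.80 | 0.56-0.58 |
| Skewed (lognormal), effect on the log scale, covariate not logged | about 0.65-0.69 | 0.54-0.58 |
| Normal, step at the median | 0.58-0.61 | 0.56-0.66 |
| Step at the 25th or 75th percentile | 0.48-0.53 | 0.31-0.39 |
| U-shape | 0.06-0.16 | 0.06-0.09 |

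The last four rows use the effect sizes of the third. With no true effect, both codings reject at about 0.05.

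**Step 4: unequal spread.** Suppose the effect is linear in each language's own SD units and the SDs differ three-fold (assumed). Centring alone then gives about 0.68-0.71, and the split 0.55-0.58. Standardising within language restores 0.79.

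**Step 5: age in 2b.** No arithmetic is needed. Three statements cannot all hold: the model has a two-level third factor, the same procedure applies to every covariate, and age is continuous with no dichotomisation note. Section 2a avoids the conflict by limiting reruns to dichotomous covariates; 2b has no such limit. As a possible remedy, a within-language permutation test of rank association with age was simulated (3,000 runs, 999 permutations, n = 20 to 40, t(3) or lognormal errors, larger error scale in one language). Type I error was 0.045-0.056 over three participant summaries, including the averaged active-minus-sham difference.

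**Step 6: floor of five.** The smallest exact two-sided Wilcoxon signed-rank p is 2/2ⁿ: 2/32 = 0.0625 at n = 5 and 2/64 = 0.03125 at n = 6. At n = 5 the normal approximation gives 0.043 uncorrected and 0.059 with continuity correction. A paired t-test on differences 1 to 5 gives 0.013.

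**The case against.** The split has a role. The by-level reruns in 2a and the factorial model in 2b both need levels, and one coding for both routes keeps results comparable across outcomes. A within-language split is also unaffected by differences in scale, which are plausible between readers of English and of Chinese characters. This stands to the extent that the split belongs in 2b and that centring alone is not enough in 2a. It does not show that 2a needs a split, because age already enters there without one.

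The size of the loss depends on an effect size the documents do not give. That stands too. A reader might infer a loss of over 20 points in general, but this holds only where the continuous analysis already has about 80% power. At r = 0.2 to 0.3 the gap is about 2 to 17 points. Nor is the split worse in every setting except a step near the median: for a U-shape neither coding detects the effect, and with a uniform covariate the two differed by less than one point.

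Critical print size is not always estimable. Protocol Day 1, step 11 assigns a test print size of 1.5 deg where no reliable elbow is found, and a continuous analysis must deal with those participants. This stands and shapes the fix.

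A reader might also infer that a group of five can never reach significance. The documents do not support that. The default follow-up is a paired t-test, and the SAP does not say that the Wilcoxon test is exact. The problem needs a group of exactly five, a by-level rerun with an interaction, a Wilcoxon route and an exact p-value.

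**Conclusion.** The point holds as a minor one, for the secondary covariate analyses only. In 2a the median split is a loss of sensitivity, not a bias. Its cost ranges from about 2 points of power for a weak linear effect to about 20 to 24 points where the continuous analysis has 80% power. It is nil, or a gain of up to 4 to 6 points, for a step at the median. These figures rest on assumed sample sizes, effect sizes and covariate shapes.

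The gap for age in 2b rests on no assumption, because the route cannot be run for age as written. It matters only for outcomes that go to 2b.

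The floor in notes b and c is a wording matter. It would be wrong to conclude from any of this that the primary analysis is compromised or that false positives are inflated.

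**What to change.** **2a, note-a covariates.** Enter critical print size and maximum reading speed as continuous covariates, centred and scaled within language, on the log scale if skewed. Enter distance acuity as continuous logMAR. Keep language in the model. Report the stimulation-by-covariate slope with a 95% confidence interval and check linearity by plot. Do not enter the default 1.5 deg as a measured critical print size; analyse that covariate only in participants with a fitted value.

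**2b, note-a covariates.** Keep the split, because ART needs a factor.

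**2b, age.** Pre-specify one within-language permutation test of the rank association between age and each participant's active-minus-sham difference averaged over the three test times, with no rerun by level. Label any test of age against the overall mean or a time contrast as exploratory.

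**Notes b and c.** Say *in each group*. Report a within-level Wilcoxon follow-up descriptively if there are fewer than six non-zero differences.

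**Cost.** SAP wording and one short permutation script, with no new data. In 2a a linear effect is then assumed, by-level reruns no longer apply to these three covariates, and the critical print size analysis may use fewer participants. Results from 2a and 2b are not directly comparable for these covariates.

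### Section 2b of the SAP tests test time and stimulation-by-time on aligned ranks with no sphericity correction, and step 1 does not say which route applies when sphericity and normality both fail

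*SAP*

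**What the plan says.** The SAP (Planned Study Components, A) crosses stimulation type, two levels, with test time: "For statistical testing, Test time will contain 3 levels, defined as" during, 5 minutes after and 30 minutes after stimulation. Under C, a stimulation-by-time interaction opens the planned contrasts, which "individually compare active vs sham at the three timepoints". Under E, "All tests will be 2-tailed with alpha = 0.05".

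Step 1 of the Analysis Procedure checks assumptions once, with the languages pooled. For sphericity it says to "use Mauchly's Test of Sphericity to check for significant violations of sphericity"; for normality, to "visually inspect pp plot and qq residual plots evaluate the degree of violation". Two routing lines follow:

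- "If sphericity assumption is violated: Use Greenhouse Giesser correction for all main effects and interactions", following section 2a. If the interaction is then significant, Wilcoxon signed-rank tests replace the t-tests.
- "If normality assumption is violated: follow *Nonparametric Statistics*, section 2b".

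Section 2b specifies an aligned rank transform (ART) ANOVA of stimulation type by test time by language, with Wilcoxon signed-rank follow-up. If language matters, it is replaced by a separate ART ANOVA for each language. No sphericity check, epsilon correction or covariance structure is given for any of these.

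**The concern.** Neither routing line is conditional on the other. Data that fail both checks meet one instruction to stay in 2a with a correction and another to move to 2b.

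If 2b is followed, a second gap opens. Ranking does not make the variances of the differences between time points equal, so the F tests on the three-level factor can still be too liberal. The plan recognises this problem in 2a and corrects for it there, but not in 2b.

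What is at stake is the interaction test that decides whether the three active-versus-sham contrasts are run. The procedure is repeated for three outcomes and for each secondary covariate. The normality trigger is a visual judgement without a threshold, so the choice of route is also partly discretionary.

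**Working it through.** **Inputs from the SAP.** Two-sided alpha 0.05; three test-time levels; the interaction as gate; a Mauchly trigger for sphericity; a visual trigger for normality. There is no sample size, SD, error shape or power figure, so there is no stated figure to reproduce. Everything numerical below rests on assumed values.

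**Step 1. Routing, case by case.**

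- Both assumptions acceptable: 2a.
- Only sphericity fails: 2a with Greenhouse-Geisser.
- Only normality fails: 2b.
- Both fail: both lines apply, and no precedence is written.

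**Step 2. What the correction does to a given F.** With two language groups the interaction F has degrees of freedom (2, 2(n-2)). Greenhouse-Geisser changes these to (2e, 2(n-2)e), where e lies between 1/(3-1) = 0.5 and 1. For assumed n = 20, 2(n-2) = 36. With two numerator degrees of freedom, p = (1 + F/18)^(-18), so an uncorrected p of 0.040 corresponds to F = 18 × (0.04^(-1/18) - 1) = 3.52. The same F gives:

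- e = 0.75, df (1.5, 27): p = 0.056
- e = 0.6, df (1.2, 21.6): p = 0.068
- e = 0.5, df (1, 18): p = 0.077

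The corresponding values are 0.057, 0.070 and 0.080 at n = 12, and 0.055, 0.067 and 0.075 at n = 30. A borderline gate can therefore open or close on the correction alone.

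**Step 3. False-positive rate of the interaction test.** Simulated change from a shared pre-test, no true interaction, n = 12 to 30, errors t(3), Laplace or lognormal:

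- During-stimulation SD twice the others: uncorrected 2b about 6-7%; with the epsilon of the aligned ranks, about 5%.
- Three times the others: uncorrected about 7-9%; with epsilon, about 6-7%.
- 2a with Greenhouse-Geisser in these settings: 3-5%.

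A repeat of this design with 2,000 replicates per setting gave slightly higher figures: 6-8% and 8-11% uncorrected, 5-7% and 7-9% with epsilon.

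**Step 4. Harsher assumptions.** With error scales across the three times of 1:1:3 and 0.5:0.5:3, t(3) or lognormal errors and 4,000 replicates per setting, uncorrected 2b rejected 9-18% of true nulls and 2a with Greenhouse-Geisser 2.9-4.8%. Epsilon on the ranks lowered 2b to 7-14%. Analysing the ranks with a random-intercept mixed model gave 9.1-18.5%, so the SAP's description of 2b as a mixed effects ANOVA does not by itself close the gap.

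**Step 5. How often both checks might fail.** With non-normal errors and sphericity true, Mauchly's test was significant in 7-34% of datasets (n = 12 to 30). At n = 20 with an SD ratio of 2 it was significant in 51-53%. The visual normality judgement was not modelled, so these are not frequencies of the both-fail case.

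**Step 6. How much is due to the missing correction.** At n = 20, given a significant Mauchly test and an assumed effect of one test-noise SD during stimulation only, 2a with Greenhouse-Geisser and uncorrected 2b disagreed in 13-29% of datasets. With epsilon on the ranks they still disagreed in 11-26%. Adding the correction changed the 2b verdict in only 3-6% of those datasets, and in about 1% when there was no effect.

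**The case against.** The strongest reply is that the text already has a sensible reading. The normality line comes last, carries no condition and is the only way into 2b. Staying in 2a after normality has failed would defeat the purpose of 2b. The list layout is also damaged in the available text, so little should rest on how the bullets are arranged. This largely stands: the precedence gap is close to a clarification. But that reading leads straight into 2b, where sphericity is not handled.

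Four stronger inferences are tempting, and the documents do not support them.

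- *The routes are contradictory, and that is what puts the result in doubt.* The 13-29% disagreement in Step 6 is mostly the ordinary difference between a raw-score and a rank test. When Mauchly was not significant, the two still disagreed in 11-17%.
- *2b ignores a violation that has just been detected.* Mauchly is run on raw scores, while 2b tests ranks. Where the raw test was significant, the ranks also failed in only 27-50% of datasets (SD ratio 1) and 43-48% (ratio 2).
- *The whole efficacy conclusion depends on the route's handling of sphericity.* Stimulation type has two levels, so sphericity does not bear on its main effect. Follow-up tests are Wilcoxon on both routes.
- *The inflation is serious in this trial.* It needs markedly unequal variances across time points, and the documents give no SDs from which to judge that.

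**Conclusion.** The point holds in limited form. Step 1 should name the route when both checks fail, and 2b should handle sphericity as 2a does. As written, 2b's interaction test is mildly anti-conservative when variances differ across time: about 6-7% at an SD ratio of 2 and 7-9% at a ratio of 3, against a nominal 5%. It is worse under the harsher scale ratios. The sizes depend on assumed n, error shape and SD ratios. Exposure is confined to the F tests for test time and for interactions with test time. Severity is minor to moderate. This is a cheap improvement and not a defect that must be repaired before the analysis can be interpreted.

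**What to change.** Replace the two routing lines with one ordered rule, fixed before unmasking:

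1. Judge normality first.
2. If it is acceptable, use 2a, with Greenhouse-Geisser when sphericity fails.
3. If it is not, use 2b whatever Mauchly's test shows. In 2b, apply the Greenhouse-Geisser epsilon computed from the aligned ranks to every F test involving test time, including the separate-language and covariate analyses.

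Epsilon on the ranks reduces the inflation but does not fully remove it under strong heterogeneity. So add a multivariate or permutation test of the stimulation-by-time interaction as a named sensitivity check whenever 2b is used.

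The cost is a few sentences in the SAP, one extra test per outcome on the 2b route, and a very small loss of power in 2b when sphericity holds.

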Improving Vision in Adults With Macular Degeneration, Study 1: the Effect of Brain Stimulation

Study Protocol Outline

Date Approved by Researchers: September 19, 2019

Inclusion Criteria

- Diagnosis of AMD (age 60+) or JMD (current age 18+).
- Central vision loss and use of a PRL (confirmed by a microperimeter).
- Visual acuity (VA); between 0.5 and 1.0 logMAR inclusive (6/18-6/60) in the better eye.
- Best-corrected near visual acuity of 4.0M at 40 cm or better in the better eye
- Stable vision for the previous 3 months (by patient report).

Exclusion Criteria

- Diagnosed dementia.
- Not fluent in reading English (Waterloo) or Chinese characters (Hong Kong).
- any ocular surgery (including anti-vegF injections) within the duration of the study.
- Ocular pathology other than JMD or AMD that can reduce central vision.
- Severe hearing impairment.

Contraindications for tDCs:

- Suffer from epilepsy, have had an epileptic seizure, or family history of epilepsy.
- Any metal implant (excluding tooth fillings).
- Implanted medication pump or implanted electronic device, including pacemaker or defibrillator
- Heat disease, neurological condition, or have had neurological or cardiac surgery.
- Recurring headaches
- Skull fracture or head injury
- Head or Brain surgery
- Pregnancy
- Skin Condition
- Taking any medication on the list on Form A
- Excessive alcohol (>2 standard drinks) or slept dramatically less the usual in the last 24 hours.

Protocol Outline

Day 0: Pre-Screening

1. Potential participants are recruited
 - Done by clinician for privacy and also to make an initial assessment about eligibility.
 - Diagnosis of AMD or JMD with VA in the inclusion range
 - Age ≥ 18
 - No diagnosis of dementia
 - No other eye disease or condition affecting vision
 - No indication of being not fluent reader in tested language
2. Call potential participants to recruit.

Day 1: Screening and RSVP baseline selection

1. Consent form and signature
2. Refraction
3. Distance ETDRS acuity.
4. Near VA (MNREAD with stopwatch) and with +4D in trial frame).
5. Decide on eye to be used (eye with better near reading vision)
6. Ocular health check (of the eye to be used)
7. PRL measure with microperimetry
8. If better eye has another ocular disease or not a stable PRL, check the poorer eye for eligibility and use that for all further testing

If patient qualifies for main study:

10. Full RSVP test [45+ minutes]

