 - 5 print sizes by 5 reading speeds, selected based on the MNREAD test results.
11. Select single print size and word speed combination that is predicted to elicit 55% with the following procedure:
 - Fit a two-line function and a simple linear regression to the data
 - i. If two-line fit is better (a CPS/ “elbow” was found):
The CPS defines the print size and word speed to be used
 - ii. If simple linear regression is better (no reliable “elbow” found):
Use print size of 1.5 deg x-height and corresponding reading speed
12. Blind-selection of stimulation codes to determine active/sham schedule for participant
 - Active/sham stratified by:
 - i. VA – [0.5, 0.8) and [0.8, 1.0] logMAR groups, to be balanced as far as stimulation schedule

NOTE: JMD participants will not be stratified by VA, but active/sham schedules will be balanced for JMD participants.

Treatment Days: *(treatment days must be separated by 2 – 14 days, otherwise redo baseline measures.)*

- Order of crowded and uncrowded tests is randomized on a per-subject basis but maintained throughout testing for each patient.
 - Setup consists of two computers. One computer 3 meters away for the crowded and uncrowded Landolt C test, and one computer on an independently rolling cart. The RSVP task will be done on the rolling computer, and then will be moved out of the way for the participant to do the Landolt C tests. This allows older patients to not be required to move continuously for these tests.
1. Primary outcomes pre-test.
 - a. specifically-selected RSVP condition tested.
 2. Secondary outcomes pre-test. Computer is fixed 3 meters away.
 - a. Crowded Landolt C
 - b. Uncrowded Landolt C
 - c. Manually calculate measure of crowding strength:
 3. Stimulation (either active or sham) for 20 minutes.
 - a. During stimulation: specifically-selected RSVP condition tested
 - b. During stimulation: Crowded and Uncrowded Landolt C
 4. Five minutes after stimulation end:
 - a. Specifically-selected RSVP condition tested
 - b. Crowded and Uncrowded Landolt C tested
 5. Thirty minutes after stimulation end:
 - a. Specifically-selected RSVP condition tested
 - b. Crowded and Uncrowded Landolt C tested

6. Participant fills out a brain stimulation adverse-effects questionnaire.
7. ONE THE FINAL TREATMENT DAY: administer blind MoCA cognitive test for use in sensitivity analysis/as a covariate

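### The active/sham schedule is balanced in the protocol but appears in no SAP model or planned comparison: a small avoidable loss of power, not a validity error

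*SAP*

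**What the plan says.** **Allocation.** Protocol, Day 1 step 12, reads "Blind-selection of stimulation codes to determine active/sham schedule for participant". The same step sets up two acuity bands as "logMAR groups, to be balanced as far as stimulation schedule". It adds that "active/sham schedules will be balanced for JMD participants". Order is therefore a designed and balanced feature of this within-subject trial.

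**Analysis.** SAP 2a.1.i reads "Perform repeated-measures ANCOVA, with Language as covariate". The factors are stimulation type and test time. SAP 2b.1.i uses the same two factors plus language after an aligned rank transform (ART). The planned comparisons are within-subject t-tests (2a) or signed-rank tests (2b), run only if stimulation and test time interact. Schedule, session and period are absent from the factors (section A), the seven covariates (section D), every step of 2a and 2b, and the participant summary table. SAP E.2 drops participants with incomplete data.

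**Prior exposure to the tasks.** RSVP is the primary outcome. Its Day 1 step is "Full RSVP test [45+ minutes" long, with "5 print sizes by 5 reading speeds, selected based on the MNREAD test results". The Landolt C tests come under "Secondary outcomes pre-test. Computer is fixed 3 meters away" on treatment days, and no Day 1 Landolt C test is listed.

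**The concern.** When order has been balanced by design, the usual course is to let the analysis use it. If participants change differently within the second session than within the first, for example because practice is levelling off, the active-minus-sham difference moves up in one schedule and down in the other. An analysis that ignores schedule treats that systematic spread as random noise. With balanced schedules the estimate is unaffected, but the test becomes conservative and some power is lost. What is at stake is efficiency in the full-set tests. In subgroup splits where schedule may happen to be unbalanced, there is also an imbalance that the reader cannot see.

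**Working it through.** **Inputs.** From the documents: alpha 0.05 two-sided (SAP E.3); change from the same day's pre-test at three test times (my reading of SAP A.2); balanced schedules (Protocol, Day 1 step 12). Not in the documents, and so assumed: sample size n, SD, effect size, one active and one sham session, and the size of any shift. The plan states no power figure to reproduce.

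**Model.** For each participant, D = active change − sham change = τ ± π + e. The sign follows schedule, SD(e) = 1, and π is the session-2 minus session-1 shift in the change score, in units of that SD.

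- Bias of mean(D) = π × (n1 − n2)/n, which is 0 when n1 = n2.
- Expected variance without schedule, balanced = 1 + π² × n/(n − 1), on n − 1 df. With schedule it is 1, on n − 2 df.
- At n = 20: 1 + 0.0625 × 20/19 = 1.07 at 0.25 SD, and 1 + 0.25 × 20/19 = 1.26 at 0.5 SD.

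**Full set, n = 20 balanced, τ = 0.66 (80% power for the paired t-test), by simulation:**

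| Shift (SD) | Power without schedule | Power with schedule | Type I error without schedule |
|---|---|---|---|
| 0 | 0.80 | 0.80 | 0.05 |
| 0.25 | 0.78 | 0.80 | 0.044 |
| 0.5 | 0.72 | 0.80 | 0.029 |

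Results at n = 12, 30 and 40 are within about 1 point of these.

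**The interaction test that opens the planned comparisons.** Only shift that varies over test times enters its error term. A shift equal at all three times left power unchanged (0.88 v 0.88). With a shift rising over test times as practice would produce, the loss was under 1 point at 0.25 SD and 2 to 4 points at 0.5 SD (0.65–0.67 v 0.69).

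**How large could a shift be?** The same-day pre-test removes a constant or linear practice gain. Take exponential practice with time constant c tests, four tests a day and k0 earlier tests. The share of the learnable gain that survives at test j is exp(−k0/c) × (1 − exp(−j/c)) × (1 − exp(−4/c)), averaged over j = 1, 2, 3.

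- No earlier exposure (Landolt C): 0.24, 0.085 or 0.017 for c = 4, 8 or 20. A 0.25 SD shift then needs a learnable gain of 0.25/0.24 ≈ 1.0, 2.9 or 15 SDs.
- With the 25 Day 1 RSVP conditions counted as 25 earlier tests: 0.005 or less. A 0.25 SD shift would need at least 0.25/0.005 = 50 SDs, which is implausible.

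**If balance is lost.** At n = 20 and a 0.5 SD shift, bias is 0.05 SD for 11:9, 0.10 for 12:8 and 0.15 for 13:7 (type I error 0.065). For the splits no schedule balancing is written. Language follows site ("Not fluent in reading English (Waterloo) or Chinese characters (Hong Kong"), and balancing by site is not stated. The SAP splits distance acuity at each language's median, not at the protocol's 0.8 logMAR boundary. For a split of 10 out of 20, the chance of 7:3 or worse is 0.18, with bias 0.5 × 4/10 = 0.20 SD at a 0.5 SD shift and type I error 0.06.

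**Side effect of a careless fix.** SAP 2b.1.iii discards the full-set analysis if language is significant or interacts with anything. A full factorial with schedule raises the language-involving tests from 4 to 8. With no true effects at n = 20, and ordinary ANOVA standing in for ART, the chance of a false trigger rises from about 0.18 to 0.33. Without language-by-schedule terms it stays at 0.19.

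**The case against.** The strongest reply is that the design already does the work. Order is balanced, each session has its own baseline, and the full-set test errs on the conservative side. For the primary outcome a shift that matters is implausible. For Landolt C even a 2-point loss needs practice gains of 1 SD or more, which nothing in the documents supports. The interaction test loses less still. All of this stands, and it limits the point to a minor improvement.

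Two further objections also stand. One degree of freedom is the price only with two schedules. The protocol does not give the number of treatment days; with two active and two sham days in any order (assumed), six schedules would use 5 df and power with no shift would fall from 0.80 to 0.73 at n = 12 and to 0.78 at n = 20. And replacing the signed-rank test by a rank-sum test on day differences does not pay at n = 20: power is 0.75 v 0.78 with no shift, 0.75 v 0.76 at 0.25 SD, and better only at 0.5 SD (0.75 v 0.69).

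The objection does not remove the omission itself, nor the fact that with two schedules the remedy costs almost nothing.

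**Conclusion.** The omission is real, and its consequence is a small possible loss of power: 0, about 2 and about 8 points at shifts of 0, 0.25 and 0.5 SD for a single active-sham contrast. It is probably negligible for RSVP and more possible for crowded and uncrowded Landolt C. These sizes rest on an assumed n, SD and shift and on two sessions. The statement that the full set is unbiased requires that the schedule balance survives the complete-case exclusion in SAP E.2 and that there is no differential carry-over.

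A reader might infer that ignoring order biases the main comparison or invalidates its p-values. The documents do not support that, because under the stated balance the estimate is unbiased and the test conservative. A reader might also infer that the subgroup splits have inflated type I error. That is true only conditional on an unlucky imbalance. Averaged over allocation the bias is zero and the overall error stays below 0.05 (for 10 of 20, 0.047 and 0.040 at shifts of 0.25 and 0.5 SD). This is a minor efficiency improvement, not a validity error.

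**What to change.** - **SAP 2a.1.i:** add schedule as a between-subject factor with its interactions with stimulation and test time, and with no language-by-schedule terms.
- **SAP 2a.1.ii:** at each timepoint, take the active-sham contrast as the mean of the schedule means. With balance this leaves the estimate unchanged.
- **SAP 2b.1.i:** if schedule is added to the ART model, leave language-by-schedule terms out of the model or out of the 2b.1.iii trigger.
- **SAP 2b.1.ii:** keep the signed-rank test as the main test. A rank-sum test on day differences is at most a sensitivity analysis.
- **Reporting:** give schedule counts for the analysed full set and for every split (language, distance acuity at the per-language median, print size, reading speed, MoCA, AMD type). Give schedule-adjusted split estimates as sensitivity analyses only. Required adjustment in small unbalanced splits would be expensive: with no shift, power falls from 0.80 to 0.72 at 7:3 and to 0.54 at 4:1.

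**Cost:** SAP wording only, since schedule is known from the stimulation codes. With two schedules it uses one degree of freedom; with no shift, power goes from 0.80 to 0.79 at n = 12 and stays at 0.80 at n = 20. With more than two schedules the cost is higher, so use a session (period) term or a sensitivity analysis instead.
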